2. STUDY DESIGN

[figure not shown]
This study is a Phase 2, multicenter, randomized, double-masked, dose-ranging, vehicle-controlled, parallel-group clinical trial. Subjects 18 years of age and older with a diagnosis of dry eye disease and experiencing an episodic flare up who meet all study entry criteria will be enrolled. The investigator and his/her staff will not know which study medication the subject is receiving but will be able to determine this in the event of an emergency.

Prior to enrollment, the study will be discussed with prospective subjects and those wishing to enter will be asked to give written informed consent. Informed consent will be obtained prior to any study related procedures being performed. Once informed consent has been obtained, the subjects will be questioned regarding their medical history to determine whether or not they are in satisfactory health to enter the study and to determine if they meet the specific entry criteria.

There will be a total of 7 study visits:

Screening Visit 1 (Day -14 to Day 0), Baseline/Randomization Visit 2 (Day 1), Visit 3 (Day 8), End of Treatment Visit 4 (Day 15), Visit 5 (Day 28), Visit 6 (Day 49) and Study Completion/Early Discontinuation Visit 7 (Day 70).

Study Visit Schematic

*Subjects who discontinue the study during the dosing period (Day 1 through Day 14) will be asked if they would be willing to return to the study site two weeks (\pm 2 days) from the last dose of study drug for the Visit 7/Early Discontinuation Visit, for subject safety. If the subject is willing to return in two weeks for the Visit 7/Early Discontinuation Visit, the subject will be discontinued from the study following the completion of the Visit 7/Early Discontinuation Visit. If the subject is not willing to return in two weeks for the Visit 7/Early Discontinuation Visit, the subject will be discontinued from the study at the current visit and all Visit 7/Early Discontinuation assessments will be performed during the current visit.

Screening (Day -14 to Day 0), Randomization (Day 1), and Dosing Phase (Day 1 to Day 14):

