During the screening phase of the study, subjects who meet all inclusion and none of the exclusion criteria will be randomized in a 1:1:1 ratio: 40 subjects in the 0.02% BSP group, 40 subjects in the 0.04% BSP group, and 40 subjects in the vehicle group. During the dosing phase (Day 1 to Day 14), subjects will instill study drug BID for 14 days. Subjects will receive instructions for dosing at home and for completing a Study Drug Dosing Diary with Drop Comfort Questionnaire during the study dosing phase (Day 1 to Day 14). Subjects (or their caregivers) will be instructed to store the study drug at room temperature (15°- 25°C; 59° - 77°F), to protect the study drug from light and to not freeze the study drug, as well as to instill 2 doses (preferably 8-12 hours apart) every day for 14 days in the study eye and the fellow eye, if applicable. The fellow eye can only be dosed if it was determined by the investigator at baseline that the fellow eye requires relief of dry eye symptoms as well. The fellow eye must follow the same dosing regimen as the study eye.

Visit 3 (Day 8)

Subjects will be assessed for safety and efficacy assessments.

Visit 4 (Day 15): Improvement

Subjects who achieve a 1 unit or better improvement in University of North Carolina (UNC) Dry Eye Management Scale (DEMS) score and a 0.5 point or better improvement in conjunctival hyperemia at Visit 4 (Day 15) when compared to their baseline scores will then be followed for 8 weeks during the evaluation phase (Day 15 to Day 70) to assess for a rebound and safety.

Rebound Assessments at Visit 5 (Day 28), Visit 6 (Day 49), and Visit 7 (Day 70)

Rebound is assessed at Visit 5 (Day 28), Visit 6 (Day 49) and Visit 7 (Day 70) when compared to Visit 4 (Day 15) as a 1 unit or more worsening in UNC DEMS score and a 0.5 point or more worsening in conjunctival hyperemia. Subjects who meet this definition of having a rebound will complete the current visit (either Visit 5 [Day 28], Visit 6 [Day 49] or Visit 7 [Day 70]) and then be discontinued from the study prior to receiving another possible treatment.

Subjects will be instructed to bring all their study drug (used and unused) and subject diaries with them to Visit 3 (Day 8) for review with site staff, and to return their study drug (used and unused) and subject diaries at Visit 4 (Day 15).

Visit 4 (Day 15): No Improvement - Early Discontinuation

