Subjects who do not achieve a 1 unit or better improvement in UNC DEMS score and a 0.5 point or better improvement in conjunctival hyperemia at Visit 4 (Day 15) when compared to their baseline score will complete the Early Discontinuation Visit (Visit 7).

Subjects' safety will be evaluated throughout the study. The safety parameters to be assessed are the incidence, severity, and relationship of adverse events (AEs) and serious adverse events (SAEs), discontinuations due to AEs, changes in visual acuity (VA) and intraocular pressure (IOP), and biomicroscopic and ophthalmoscopic findings in treated eyes.

Efficacy will be assessed as follows: All analyses will be done descriptively. No confirmatory statistical testing will be performed, but exploratory statistical tests may be used to evaluate the efficacy parameters. Data for the study eye will be used for all efficacy analyses.

Primary Efficacy Analysis:

The primary efficacy analysis planned is listed below. Each active treatment group (0.02% and 0.04% BSP) will be independently compared to the Vehicle group. As this is a Phase 2 study, no superiority claims are being tested; therefore, no adjustments will be made for multiple comparisons. Comparisons will be made with a two-sided Fisher's exact test with an alpha-level of 0.05.

1. The proportion of subjects with clinically significant improvement from baseline in UNC DEMS score at Visit 3 (Day 8) will be summarized for each treatment group. A clinically significant improvement is defined as a minimum reduction in UNC DEMS score of 1 unit or more. Subjects who receive another therapeutic treatment for the signs and symptoms of their episodic flare up due to a lack of efficacy at or prior to Visit 3 (Day 8) will be treated as failures.

Secondary Efficacy Analyses:

The two secondary efficacy analyses planned are listed below.

1. The proportion of subjects with clinically significant improvement from baseline in UNC DEMS score at Visit 4 (Day 15) will be summarized for each treatment group. A clinically significant improvement is defined as a minimum reduction in UNC DEMS score of 1 unit or more. Subjects who receive another therapeutic treatment for the signs and symptoms of their episodic flare up due to a lack of efficacy at or prior to Visit 4 (Day 15) will be treated as failures.

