8. CLINICAL ASSESSMENTS/EXAMINATION PROCEDURES

Assessments Completed by Subjects:

UNC DEMS Questionnaire: The UNC DEMS will be completed by subjects at Visit 1 (Screening; Day -14 to Day 0) and only at Visit 2 (Day 1, prior to randomization) if Visit 2 is >5 days following Visit 1. The UNC DEMS will also be completed by subjects at Visit 3 (Day 8) through Study Completion/Early Discontinuation Visit 7 (Day 70).

Dosing Diary with Drop Comfort Questionnaire: Subjects will be given a Dosing Diary with Drop Comfort Questionnaire to record study drug dose instillation dates and times for each dose, as well as to record their responses to the Drop Comfort Questionnaire twice weekly during the dosing period (Day 1 to Day 14).

Assessments Completed by Investigators:

Best-Corrected Visual Acuity (BCVA): BCVA will be performed in both eyes at Visit 1 (Screening; Day -14 to Day 0) and only at Visit 2 (Day 1, prior to randomization) if Visit 2 is >5 days following Visit 1. BCVA will also be performed in treated eyes at Visit 3 (Day 8) through Study Completion/Early Discontinuation Visit 7 (Day 70). Log of the minimum angle of resolution (logMAR) score using ETDRS (Early Treatment Diabetic Retinopathy Study) chart will be used to measure BCVA. Performing a pinhole test is allowed as long as its use remains consistent for the same subject throughout all study visits.

Biomicroscopy: Slit lamp biomicroscopy will be performed to observe the overall health of the eye, including the lid/lashes, conjunctiva, cornea, anterior chamber, iris, and lens. This will be performed in both eyes at Visit 1 (Screening; Day -14 to Day 0) and only at Visit 2 (Day 1) if Visit 2 is >5 days following Visit 1. Slit lamp biomicroscopy will also be performed in treated eyes at Visit 3 (Day 8) through Study Completion/Early Discontinuation Visit 7 (Day 70).

Ophthalmoscopy: An ophthalmoscopy examination will be performed in both eyes at Screening Visit 1 (Day -14 to Day 0) and in treated eyes at End of Treatment Visit 4 (Day 15). If anesthesia is used to perform the ophthalmoscopy examination, symptom assessments will be completed first before anesthesia administration or dilation.

Intraocular Pressure (IOP): IOP will be measured in both eyes at Visit 1 (Screening; Day -14 to Day 0) and only at Visit 2 (Day 1) if Visit 2 is >5 days following Visit 1. IOP will also be measured in treated eyes at Visit 3 (Day 8) through Study Completion/Early Discontinuation Visit 7 (Day 70).

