9. ADVERSE EVENTS

Throughout the course of the study, the investigator must remain alert to possible adverse events or untoward findings. If adverse events occur, the first concern will be the safety of the subject. Appropriate medical intervention will be provided by the investigator.

Adverse Event (AE) Definition: An AE is any untoward medical occurrence associated with the use of a study drug in a clinical investigation subject, whether or not considered related to the study drug.

Adverse Event Reporting Period: The AE reporting period for this trial begins upon signing the ICF and ends at the completion of the subjects' final study visit exam. All AEs reported by the subject during the course of the study, or elicited by questions from the investigator, or noted as a result of procedures carried out on the subject, during the AE-reporting period must be recorded by site staff in the source documents and on the AE eCRF, whether or not the event is considered related to the study drug. In addition, any known untoward event that occurs subsequent to the AE reporting period that the investigator assesses as related to the study drug should also be reported as an AE.

Serious Adverse Event (SAE) Definition: A serious adverse event (SAE) or reaction is any untoward medical occurrence that at any dose:

- Results in death
- Is immediately life-threatening or immediately sight-threatening in a treated eye(s)
- Requires inpatient hospitalization or prolongation of existing hospitalization
- Results in persistent or significant incapacity or substantial disruption of the ability to conduct normal life functions
- Is a congenital anomaly/birth defect
- Is an important medical event that may jeopardize the subject or may require medical intervention to prevent one of the outcomes listed above

SAE Reporting: SAEs must be immediately reported (within 24 hours of awareness of the event) to designated contract research organization (CRO) and will be clearly documented in the source documents and on the appropriate AE eCRF and SAE Report Form. The investigator must also notify the IRB of any SAEs, according to the IRB's guidelines.

Pre-existing Conditions: In this trial, a pre-existing condition (i.e., a disorder present before the AE-reporting period started and noted on the Systemic and/or Ocular Medical History Forms) should not be reported as an AE unless the condition worsens or episodes increase in frequency or severity during the AE-reporting period.

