12. SAFETY

12.1. Adverse Events

Adverse events will be summarized separately for those occurring in the study eye, in the fellow eye, and non-ocular events. For overall AE incidence summary, one table for ocular AEs (study eye and fellow eye combined) will be reported. In this table, each subject will be counted only once in each summary category, to avoid correlated data. However, the results should be interpreted with caution because fellow eyes are selective samples by study design. Regardless of whether the fellow eye is treated or not, all AEs reported for the fellow eye will be included for the safety analysis. AEs marked as 'Both Eyes (OU)' from the AE CRF page will be summarized both for study eye and fellow eye.

All AE verbatim terms will be coded using Medical Dictionary for Regulatory Activities (MedDRA) version 23.0 Update. Terms will be coded to the full MedDRA hierarchy, but the system organ class (SOC) and preferred term (PT) will be of primary interest for the analysis.

Treatment emergent adverse events (TEAEs) are defined as AEs that first occurred or worsened on or after the date of first administration of study drug. If missing dates or time prevent a clear determination as to whether the AE is treatment emergent, the AE will be regarded as a TEAE.

While all AEs will be summarized, the main AE summaries will be restricted to TEAEs only. Treatment emergent adverse events will be summarized descriptively. For the summary of TEAEs, if a subject experienced the same AE multiple times, this will only be counted once for the purpose of counting the number of patients experiencing that AE. Summary tables will include the number of subjects (%) experiencing an AE and the number of AEs.

The TEAE summaries will include:

- Overall Summary of Subjects with at Least One Adverse Event
- Summary of TEAEs by SOC and PT
- Summary of TEAEs with an Incidence $\geq 5\%$ by SOC and PT
- Summary of Serious TEAEs by SOC and PT

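### Adverse-event observation after Day 15 depends on response, but the listed TEAE tables give one crude percentage per arm over the whole period

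*Combined protocol and SAP*

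**What the plan says.** All references are to the combined protocol and SAP.

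**Who is observed, and for how long (Section 2).** Subjects meeting both Day 15 improvement criteria, UNC DEMS and hyperemia, "will then be followed for 8 weeks during the evaluation phase (Day 15 to Day 70) to assess for a rebound and safety". Those who rebound complete the visit at which this is found "and then be discontinued from the study prior to receiving another possible treatment". Subjects who do not meet the improvement criteria "when compared to their baseline score will complete the Early Discontinuation Visit (Visit 7").

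**When events are collected (Section 9).** "The AE reporting period for this trial begins upon signing the ICF and ends at the completion of the subjects' final study visit exam". After that, the investigator should still report "any known untoward event that occurs subsequent to the AE reporting period that the investigator assesses as related to the study drug".

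**How often subjects are examined (Section 8).** For pressure: "IOP will also be measured in treated eyes at Visit 3 (Day 8) through Study Completion/Early Discontinuation Visit 7 (Day 70"). Visual acuity and slit lamp follow the same schedule. Under Section 9, some findings at these examinations are themselves adverse events, among them a 10 mmHg pressure rise from baseline or from any earlier visit.

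**How events are tabulated (Section 12.1).** TEAEs are "AEs that first occurred or worsened on or after the date of first administration of study drug". The tables give the number and percentage of subjects and the number of events. Section 10.3 defines the safety population as everyone dosed, and Section 10.5 makes the relevant population the default denominator. None of the four TEAE tables listed has a period split, subjects at risk or person-time. The text supplied ends inside that list.

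**The concern.** Two outcomes that treatment is meant to change, improvement at Day 15 and later rebound, determine how long a subject is watched for adverse events. Randomisation does not balance a quantity fixed by post-randomisation response. A single percentage per arm over the whole period then mixes how often events happen with how long subjects were observed, and event counts have the same weakness.

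Detection differs too. A full-term improver is examined at five post-baseline visits, a non-improver at two or three.

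Safety is a stated objective of this dose-ranging study (Section 1), so the columns will be read side by side. From these tables a reader could not tell a drug effect from unequal observation, and a real excess could be hidden if the active arm is observed for less time.

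**Working it through.** The documents state no event, improvement or rebound rate, so there is no planned figure to reproduce. **All rates below are assumptions.** From the documents come 40 subjects per arm (Section 4) and the visit days 15, 28 and 70 (Section 2).

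**Model.** The hazard is the same in both arms: 0.005/day to Day 15 (15 × 0.005 = 0.075), then *h* per day. *r* is the share improving, *q* the share of improvers leaving at Day 28, and *E* the last day for non-improvers.

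Crude % = r[(1−q)(1−e^(−0.075−55h)) + q(1−e^(−0.075−13h))] + (1−r)(1−e^(−0.075−(E−15)h)), where 55 = 70−15 and 13 = 28−15.

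**Base case** (r = 0.7 v 0.4, q = 0, E = 15, h = 0.005):
- Full-term improver: 1−e^(−0.35) = 29.53%. Non-improver: 1−e^(−0.075) = 7.23%.
- Better-responding arm: 0.7 × 29.53 + 0.3 × 7.23 = 22.84%.
- Other arm: 0.4 × 29.53 + 0.6 × 7.23 = 16.15%.
- Gap 6.69 points, or 0.0669 × 40 = 2.7 subjects. SE = √(0.2284×0.7716/40 + 0.1615×0.8385/40) = 8.83 points.
- Mean observation: 0.7×70 + 0.3×15 = 53.5 days v 0.4×70 + 0.6×15 = 37.0 days.

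**Gap in points (better-responding arm minus other):**

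| Scenario | h = 0.005 | h = 0.002 | h = 0.001 |
|---|---|---|---|
| Base, 70% v 40% improve | 6.69 (SE 8.83) | 2.90 (SE 7.40) | 1.49 (SE 6.69) |
| 60% v 50% improve | 2.23 | 0.97 | 0.50 |
| Base, non-improvers seen to Day 28 | 4.94 | 2.18 | 1.13 |
| Base, 25% of non-improvers' later events still reported | 4.84 | 2.14 | 1.11 |
| Base, 30% of improvers leave at Day 28 in both arms | 5.21 | 2.24 | 1.15 |
| 70% v 40% improve, rebound 70% v 10% | −0.72 | −0.38 | −0.21 |

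With h = 0 both arms show 7.23%. Equal improvement and rebound also give no gap.

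**Other direction.** The last row is 14.77% v 15.49% at h = 0.005. With 60% v 50% improving, rebound of 40% v 20% gives −0.07 points and 50% v 20% gives −1.06. A separate constant-hazard model sets a 30% risk over 70 days. Improvement is 60% v 45%; active improvers leave 70% at Day 28 and 10% at Day 49, vehicle improvers 10% at Day 28. It gives 13.5% v 16.8% at equal hazard. There, a true hazard ratio of 1.25 would appear as 16.4% v 16.8%.

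**Detection.** With one pre-dose value and *n* later visits, the pressure rule allows C(n+1, 2) comparisons: 15 for five visits, 3 for two, 6 for three.

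**Would person-time alone be enough?** Not if the hazard falls after dosing. Take 20% risk by Day 15 (cumulative hazard 0.2231, or 0.01488/day) and one fifth of that daily hazard afterwards (0.00298), in both arms, with 60% v 30% improving:
- (0.2231 + 0.6×55×0.00298)/48.0 = 0.67 per 100 person-days.
- (0.2231 + 0.3×55×0.00298)/31.5 = 0.86 per 100 person-days.

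A table of first dose to Visit 4 over all dosed subjects gives 7.23% in both arms of the base case, if nobody drops out early.

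**Undatable events.** If 10% of late events were undated and all went into that early table, improvers would show 1−e^(−0.075−0.1×55×0.005) = 9.75%. The arms become 8.99% v 8.23%, an artefact of 0.75 points.

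**The case against.** The strongest reply is that the plan already shows timing. Section 10.5 puts all data in listings sorted by treatment group, and Section 10.6 adds study day. Section 10.5 also provides for by-visit safety summaries; those at Days 8 and 15 precede the outcome-dependent exits and so rest on equal planned observation. This deserves credit: in 120 subjects a reader could see when events arose. But neither output corrects the TEAE percentages.

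Other points, and what stands of each:
- **Size.** Every rate is assumed and every gap with an SE above is below one SE. The 6.7-point case keeps the dosing-period hazard for 55 days after a 14-day course. At h = 0.002 the base gap is 0.029 × 40 = 1.2 subjects. This limits the importance, though the distortion is systematic and runs through every all-period TEAE table.
- **Detection.** Fifteen comparisons against three is a count, not a risk. For independent normal readings with a within-subject SD of 2 mmHg, a rise of 10 mmHg in some pair occurs in about 0.3% v 0.06%; at 3 mmHg, 10% v 2.5%. The documents give no SD, so this part has no firm size.
- **Late reporting.** Known, drug-related events after the final visit are still reported. This narrows the gap without closing it.
- **Missing text.** A later table with a period split or person-time may exist.
- **Descriptive analysis.** No safety test is planned in the text supplied, so the issue is how side-by-side percentages read.

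A reader might also infer that Section 2 contradicts itself on the Early Discontinuation Visit. It does not. The two-week return is for "Subjects who discontinue the study during the dosing period (Day 1 through Day 14) will be asked if they would be willing to return", whereas the Day 15 rule concerns subjects who reach Visit 4. The timing for Day 15 non-improvers could be clarified, but that is not part of the error.

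**Conclusion.** The point holds in a limited form. The TEAE tables listed in the text supplied can show different percentages in arms with equal hazard, because observation after Day 15 depends on improvement and rebound. In the scenarios shown the gap is about 0 to 7 points either way, below one SE at 40 per arm where an SE was computed. It is zero if no events arise after Day 15 or if improvement and exits are equal across arms. These sizes rest wholly on assumed rates and a piecewise-constant hazard.

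A reader might go further and infer that the active arms will be made to look less safe. The documents do not support this: more improvement lengthens an arm's observation, more rebound shortens it, and neither rate is given. Nor do they support saying that event timing is hidden or that the SAP certainly has no such table. No stated decision rule depends on these percentages. The case for changing the plan is that a less biased comparison is available cheaply from data already collected.

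**What to change.** 1. Keep the all-period TEAE tables, since post-treatment safety is a stated purpose, and add subjects at risk and person-days by arm.
2. Add TEAE tables by arm for onset from first dose through the Visit 4 date (Day 15 if Visit 4 is missed), over all dosed subjects. Name these as the between-arm comparison.
3. Tabulate later TEAEs separately with subjects at risk and person-days, labelled as a non-randomised comparison of mainly Day 15 improvers.
4. Show TEAEs whose dates do not allow a period in a separate row. Include them in the Day 1–15 table only as a sensitivity analysis. Sections 10.4 and 12.1 settle whether such an event is treatment-emergent, not which period it belongs to.
5. Cut periods by AE start date against the Visit 4 date. Section 10.6 confines derived study day to listings, and this cut leaves that rule unchanged.

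The cost is SAP wording and a few extra tables; no new data are needed and no table is removed. Dropouts before Day 15 will still shorten observation in the Day 1–15 table. Separately, and only as a clarification, Section 2 could state when a Day 15 non-improver has the Early Discontinuation Visit, so that person-days can be planned.

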10.4. Data Handling: Handling of Missing Data

All missing data will generally not be imputed unless otherwise specified. For subjects who are withdrawn from the study prior to study completion, all data compiled up to the point of discontinuation will be used for analysis. All study discontinuations will be included in all analyses up to the time of study discontinuation.

For the classification of treatment emergent adverse events (TEAEs) and concomitant medications, the following will be applied in case of missing/incomplete dates:

- If all dates/times (start and stop) are missing, the event/medication will automatically be classified as a TEAE/concomitant medication.
- For AE/medication with a missing start date/time, if the event end date/time is prior to first study drug administration, the event will not be classified as a TEAE/concomitant medication, as applicable.
- If only the AE start year/medication end year is present and is the same or is after the first study drug administration year unit, the event/medication will be classified as a TEAE/concomitant medication, as applicable.
- If the AE start month and year/medication end month and year are present and are the same or after the first study drug administration month and year units, the event/medication will be classified as a TEAE/concomitant medication, as applicable.

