10.6. General Derived and Transformed Data

Age, in completed years, at informed consent date will be defined as: Age (years) = integer value (Date of Informed Consent – Date of Birth + 1) / 365.25).

Study day will be calculated using the first dosing date as the reference date. If the date of interest occurs on or after the first dosing date, then study day will be calculated as (date of interest – date of first dosing) + 1. If the date of interest occurs prior to the first dosing date, then study day will be calculated as (date of interest – date of first dosing). The day of the first dosing will be identified as Study Day 1 according to Clinical Data Interchange Standards Consortium (CDISC) standard. If a subject is dosed but dosing dates are missing, then the randomization date will be used as the first dosing date for the calculation of study day. Data listings will present study days in addition

to assessment dates, where applicable. As per above, all data summaries and data listings will use the nominal visit names as captured in the CRF and as per the protocol schedule of visits. The calculated study day as per CDISC will only be used in data listings to indicate the distance of an event from the dosing day.

Baseline will be defined as the last available, non-missing observation prior to the first dosing time with study drug, unless specifically mentioned otherwise. When baseline is derived, all data before the first dosing with study drug, including unscheduled visits before the first dosing with study drug, will be used for the derivation of baseline value.

Change from Baseline: Assessment value at post-dosing visit – baseline value. It should be noted that if the derived baseline as above is missing for one parameter, then the change from baseline will not be available for this parameter. Imputation of baseline data will not be conducted.

Percentage Change from Baseline:

$$(\text{Assessment value at post-dosing visit} - \text{baseline value}) * 100 / \text{baseline value}$$

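### Section 10.4 counts an adverse event that ended before the first dose as treatment-emergent when its start is known only to the month of dosing

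*Combined protocol and SAP*

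**What the plan says.** Two sections of the combined protocol and SAP decide whether an adverse event is treatment-emergent.

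Section 12.1 (Adverse Events) gives the definition: "AEs that first occurred or worsened on or after the date of first administration of study drug". Its next sentence sets a default: "If missing dates or time prevent a clear determination as to whether the AE is treatment emergent", the event is counted as a TEAE. The main AE tables are limited to TEAEs.

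Section 10.4 (Handling of Missing Data) gives four specific rules, introduced by "the following will be applied in case of missing/incomplete dates":

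1. Nothing known: "If all dates/times (start and stop) are missing, the event/medication will automatically be classified as a TEAE/concomitant medication".
2. Start missing: "if the event end date/time is prior to first study drug administration, the event will not be classified as a TEAE/concomitant medication".
3. Start known to the year: "If only the AE start year/medication end year is present and is the same or is after the first study drug administration year unit"; such an event is a TEAE.
4. Start known to month and year: "If the AE start month and year/medication end month and year are present and are the same or after the first study drug administration" (compared by month and year); such an event is a TEAE.

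For AEs, only rule 2 looks at the stop date. For medications, rules 3 and 4 test the end date; for AEs they test the start alone. No order of precedence is given among the four rules, or between Sections 10.4 and 12.1.

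**The concern.** A complete stop date before the first dose settles the question: the event cannot have begun or worsened on treatment. Rule 2 respects this and rule 4 does not. Learning the start month of such an event can turn it from not treatment-emergent into treatment-emergent, which cannot be intended.

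The situation can arise. Section 9 collects AEs from the signing of consent, and Section 2 allows screening from Day -14, so some AEs may begin and end before dosing. At stake is the content of the main safety tables, and whether two programmers working from the same text would produce the same tables.

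**Working it through.** The plan gives no figure to reproduce. The check applies the written rules to one event and compares the answers.

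**Illustrative event (dates assumed).** First dose 20 March at 09:00; AE stopped on 15 March, complete stop date recorded.

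| What is known of the start | Section 10.4, read literally | Section 12.1 alone |
|---|---|---|
| Nothing | Not a TEAE (rule 2) | Not a TEAE |
| March, same year | **TEAE (rule 4)** | Not a TEAE |
| Same year only | **TEAE (rule 3)**, if that rule applies when a stop date is known | Not a TEAE |
| February, same year | No rule applies | Not a TEAE |
| Previous year only | No rule applies | Not a TEAE |

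The event is the same in every row. Section 12.1 gives one answer throughout, because the stop date makes the determination clear. Section 10.4 departs from it in the second row and perhaps the third. The third is less certain because the word 'only' in rule 3 could mean that no other date, including the stop date, is known.

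**How often would a month-only start trigger rule 4?** Assume that every first-dose day in a 365-day year and every onset 1 to 14 days earlier is equally likely. The 14 days match the maximum screening period in Section 2.

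- Pairs of dose day and onset day: 365 × 14 = 5,110.
- If the first dose falls on day d of a month (d = 1 to 14), 15 − d of the 14 onsets fall in the previous month. Summed over d: 14 + 13 + … + 1 = 105 per month.
- Onset in the dosing month: (5,110 − 12 × 105) / 5,110 = 3,850 / 5,110 = 75.3%.
- Onset in the dosing year: (5,110 − 105) / 5,110 = 5,005 / 5,110 = 97.9%.

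So for a screening AE recorded with only a start month, rule 4 would usually apply. This says nothing about how many AEs will have such dates, which the documents do not indicate.

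**A separate point, Day 1.** Section 12.1 classifies by date; rule 2 of Section 10.4 uses date and time. Take a first dose at 09:00 and an AE that ended at 08:00 that day. With the start missing, rule 2 excludes it. With the start fully recorded as 07:30, the date-based definition includes it. This is a mismatch of units and does not cause the partial-date problem above.

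**The case against.** The strongest reply is that Section 12.1 already resolves the case: its default applies only when the status is unclear, and a stop date before dosing makes it clear. That is right about Section 12.1, but it does not remove the conflict. Section 10.4 states its rules as ones to be applied, they are the more specific text, and nothing says that Section 12.1 overrides them.

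A second reply is that a missing start in rule 2 can be read to include an incomplete one. Then rules 2 and 4 both apply to the same AE with opposite results and no stated precedence. The contradiction moves but remains.

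Several stronger readings are tempting and are not supported:

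- *Any partly known start makes a finished event a TEAE.* No. The start must match the dosing month and year, or possibly the dosing year; an earlier partial start triggers no rule.
- *Classification by date on Day 1 is an error.* Counting every first-dose-day event is a common, conservative choice. Under Section 8, dose times come from a diary that the subject completes, so classification by time could wrongly remove a true reaction to the first drop. Section 10.6 sets baseline by "last available, non-missing observation prior to the first dosing time with study drug", but that governs assessment values, not AEs.
- *Day 1 examination effects will fill the TEAE tables.* Section 8 schedules the Visit 2 tonometry, Schirmer test and staining only when Visit 2 is more than 5 days after Visit 1. They are repeated at later visits, so their effects reach the TEAE tables in any case.
- *The comparison with vehicle is diluted.* Section 12.1 summarizes TEAEs descriptively, and events before dosing should not differ systematically between randomized, masked arms.

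**Conclusion.** The point holds for rule 4 of Section 10.4. As written, it classifies as treatment-emergent an AE that a complete stop date shows was over before exposure, against rule 2 and against the default in Section 12.1. Rule 3 may share the fault, with less certainty.

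The importance is minor. The error needs three things together: a pre-dose AE, a start known only to the dosing month (or year), and a complete stop date before dosing. A few events at most is a judgment, since the documents give no rate. With 40 subjects planned per arm, one such event could move a preferred term from 1/40 = 2.5% to 2/40 = 5.0% and into the table of TEAEs at 5% or above. That needs a second subject with the same term in the same arm, and a threshold applied by arm, which Section 12.1 does not specify. Events are over-counted, not lost: Section 12.1 also summarizes all AEs and Section 10.5 lists all data. Efficacy is unaffected.

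**What to change.** In Section 10.4, put the stop-date check first: an AE with a missing or incomplete start whose complete stop date is before the date of first dose is not a TEAE. Then state that the year-only and month-and-year rules apply only to the AEs that remain. This removes only events shown to be over before dosing and keeps the inclusive default for uncertain ones.

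Separately, use one unit in Sections 10.4 and 12.1 for Day 1 events. Keeping the calendar date in both is acceptable and conservative. Classification by time is optional; if it is chosen, the plan should say what happens when a time is missing and accept its reliance on diary times.

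The cost is a sentence or two in Section 10.4 and a small programming change, best settled before unmasking. No additional data are needed.
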